## **Pre-screening at Inova Fairfax Hospital as an Activity Preparatory to Research**

Inova will refer the patients to NIH after patient signs release of information authorization. The NIH Associate Investigator and Study Coordinator will have physical access to the medical records of the Inova Advanced Lung Disease (ILD) Clinic and Pulmonary Rehabilitation Department referral patients for purposes of pre-screening Inova patients and patient referrals for this study. NIH investigators represent that (1) the use or disclosure of these records is solely to review PHI as necessary to aid study recruitment, (2) the PHI will not be removed from the covered entity (Inova Fairfax Hospital) in the course of review, and (3) the PHI for which use or access is requested is necessary for the research.

### **Pre-Screening Process in the Inova Fairfax Advanced Lung Disease Clinic:**

If NIH Associate Investigators are at Inova Fairfax Hospital and [name] or his associates at the Inova Advanced Lung Disease (ALD) Clinic feel a patient would be a good candidate for enrollment into this study based on inclusion/exclusion criteria, the NIH associate investigator will be introduced to the patient after a brief overview of the study. If the patient is interested, he or she will sign an Inova Authorization to Release and Disclose PHI form. If the patient meets initial eligibility criteria, an appointment will be made for the patient to come to NIH for NIH consent and testing.

If the NIH Associate Investigator is not at the Inova Fairfax Hospital at the time of a patient visit and [name] or one of his associates at the Inova ALD Clinic feel a patient would be a good candidate for enrollment into the study based on the inclusion/exclusion criteria, the ALD clinic research staff will introduce the patient to the study, and the research team will have the patient sign an Inova Authorization to Release and Disclose PHI form. Once the form has been signed the NIH Investigator may contact the patient directly for follow-up.

### **Pre-Screening Process in the Inova Pulmonary Rehabilitation Outpatient Department:**

Patient will sign release of record authorization then the patient will be referred to NIH Associate Investigator and Study Coordinator in the Pulmonary Rehabilitation Outpatient Clinic. Then referral records of patients referred for pulmonary rehabilitation for the purposes of prescreening for the study may be reviewed. When a possible patient is identified, the Inova Pulmonary Rehabilitation registrar will contact the patient by telephone to schedule pulmonary rehabilitation. The patient will be informed about the study and will be given the NIH Associate Investigator's contact information if the patient states they are interested. The Inova Fairfax Pulmonary Rehabilitation registrar will state the following to the patient referral after beginning the process of registering the patient for pulmonary rehabilitation:

“You may be eligible for an NIH study examining the benefits of pulmonary rehabilitation for patients with interstitial lung disease. Would you like the contact information for the NIH study coordinator for more information about the study?”

**If the NIH Study Coordinator interviews a potential subject from any source the following script will be followed:**

“Thank you for your interest regarding the research we are conducting to determine the benefits of a walking program for patients with interstitial lung disease. We are accepting volunteers between the ages of 21 and 80 who have been diagnosed with interstitial lung disease and who have been referred by their physician for pulmonary rehabilitation. If you are enrolled in the study we would ask that you come to NIH for a day of testing which would include a test to determine how far you can walk in 6 minutes, breathing tests and a treadmill exercise test. During the treadmill test you will have 16 electrodes on your chest, we will ask that you wear a neoprene mask to collect data on the amount of oxygen you breathe in and out, as well an electrode on your calf to determine the amount of oxygen your muscle utilizes for energy.

After testing you will be randomized into one of two groups, group 1 will receive exercise and education simultaneously 3 days a week for 10 weeks concluding with repeat testing at NIH. Group 2 is a 20 week group where you will receive education one day each week for 10 weeks, return to NIH for testing followed by 10 weeks of exercise 3 days a week and finally one last testing session at NIH. We do not have control over which group you are assigned to. You will be put into a group by a process called “randomization” where you have a 50-50 chance of landing in either group. Does this sound like something that you would like to participate in?”

If they answer “yes,” we ask if they have time to answer a short questionnaire that would allow us to evaluate their eligibility and safety for inclusion into the study. (Please see Appendix 2 of the protocol to compare the inclusion/exclusion criteria with the questions we would be asking.)

If, based on this interaction, we think the subject might meet the inclusion criteria for the study, we will request medical records (recent history, medication list, pulmonary function test, resting EKG, six minute walk and echo) to further evaluate their eligibility for the study. Potential participants can either send us their medical records or they can fill out a medical release document and we will request this information from their physician prior to their visit to NIH. Their medical records will be reviewed and, if it appears that the patient meets the inclusion criteria, we will set

up an appointment for the patient to come to the NIH Clinical Center for consent and testing. If, after obtaining a patient's medical records it is clear that the patient does not meet inclusion criteria, the information may be used to refine our inclusion and exclusion criteria; however, these medical records will not be used for any research purposes.

To prepare for the visit, we will enter their personal information into the NIH Admissions Travel and Vouchers system and an NIH patient number will be assigned to them. Upon arriving at the NIH, the patient will proceed through admissions and then consented to the study, followed by a history and physical, blood draw, ECG, transthoracic echocardiogram, pulmonary function testing, arterial occlusion muscle oxygenation capacity test, cardiopulmonary exercise test, questionnaires, and six minute walk test.

## **Exclusions:**

**Exclusion of Children:** Individuals younger than 21 years will not be included in the protocol because reference ranges for normative aerobic capacity and aerobic fitness have not been established for these age ranges. The objectives of this project do not include establishing these normative reference ranges. Moreover, far less is understood about advanced lung disease in children and the mechanisms by which it occurs. This lack of information could introduce critical levels of bias into the interpretation and cause the interpretation of our results to be misleading. Exercise response and adaptation in children with advanced lung disease should be studied in separate and specific protocols.

## **Exclusion of Pregnant Women:**

Women of childbearing age will undergo urine pregnancy testing during screening and follow-up visits and will be excluded from the study should results be positive. Pregnant women will necessarily be excluded from the study for safety reasons. Women who do not exercise before pregnancy should not begin a rigorous exercise during pregnancy and would not be able to achieve the target heart rate required as part of the testing and training.

## **Exclusion of Those Who Are Unable to Obtain Informed Consent:**

Individuals unable to give informed consent will necessarily be excluded from the study because of the risk to subject safety and the need to maintain integrity of the study. Subjects must be able to comprehend and follow directions, and express their own needs adequately during all testing and retesting procedures, and exercise and educational training sessions.

## **Benefits and Risks/Discomforts:**

A previous study found that participation in an aerobic exercise training program improved 6MW distance, peak VO2, and resting pulmonary artery systolic pressure. No less is expected for patients completing the proposed study. In particular, 6MWD has been used as an endpoint in

clinical trials of medications used to treat advanced lung diseases because it correlates indirectly with the mortality and may correlate directly with quality of life.

The risks of this study are those associated with aerobic exercise testing and training in patients who have circulatory disorders. These include sudden cardiac arrest, myocardial infarction, angina and electrocardiographic abnormalities, shortness of breath, dizziness, early onset of fatigue and exhaustion, near-syncopal or syncopal episodes, and muscle or joint pain. Many of these symptoms may occur during the immediate, post-exercise recovery phase, which is generally thought to be the first six minutes following strenuous exercise. Risk of injury also includes those related to falling on a moving treadmill belt such as abrasions, contusions, cuts, sprains, fractures, or muscle strain. The likelihood that any of these injuries would occur is small and preventive measures will be enforced to insure that the risks remain at a minimum.

Many subjects will experience delayed onset muscle soreness after the treadmill exercise tests or after beginning the exercise-training phase. This soreness will be mild to moderate in intensity and may be felt immediately after exercise or up to 48 hours following the exercise session. It will typically subside within seven days. Many subjects will also experience increased levels of fatigue that are sustained for up to 24 hours following the exercise sessions. This fatigue will typically subside after one to three weeks.

In order to minimize the possibility of an attack exacerbated by the arterial occlusion muscle oxygenation capacity test, subjects diagnosed with severe Raynaud's phenomenon will be excluded from participation in that test. Otherwise, the risk of exercise in this population is similar as for other ILD patients. These subjects were exercised safely with no adverse events in our previous study examining the benefits of exercise in patients with pulmonary hypertension. Included in that study were patients with ILD with connective tissue disorders who had Raynaud's [56].

Subjects with uncomplicated diabetes will be monitored before and after exercise testing and training for glucose levels and glycemic responses to exercise. Physical activity generally reduces glycemic levels and intense activity can cause transient blood glucose elevations in individuals with diabetes. Thus, the risks of hypoglycemia and hyperglycemia are associated with exercise in individuals with diabetes. The acute risks of exercise for individuals with diabetes must be weighed against the potential long-term benefits such as a reduction in cardiovascular disease risk and improved hemodynamic function. In order to reduce risks and avoid the onset of diabetic symptoms during participation in the study, glucose monitoring will be performed per standard of care.

Exercise is a very low risk intervention in this population. The most serious risks for those participating in exercise are cardiovascular abnormalities. These risks are slight even in individuals with known coronary atherosclerosis during maximal exercise testing. In studies that include known heart disease as well as patients in whom the presence of heart disease is unknown, morbidity and mortality during maximal exercise testing remains low at 0.0 to 8.3 per 100,000 and 0.0 to 1.0 per 100,000 respectively[53-62]. Morbidity and mortality remain at similar lows for maximal exercise testing environments that are attended by a physician and those supervised by a physician but operated without physician attendance [54, 57, 60, 63, 64]. Exercising at sub-maximal intensities carries with it even lower risk of adversity. Therefore, we would consider a **single study related death, myocardial infarction, or stroke** to be a reason to consider stopping the study. Should one of these *unanticipated serious* adverse events occur, the PI will notify the

Clinical Director, IRB, and our independent medical monitor within the time frame and according to the policies specified in the currently approved NIH OHSRP SOP Policy 801 (“Reporting Research Events”). Following the completion of the SAE review and the determination of the IRB we will consider stopping the protocol if the IRB deems it necessary.

To minimize risk and maximize safety, exercise tests and classes will be carried out in laboratories that are in clinical settings with immediate response backup at the NIH Clinical Center and Inova Fairfax Hospital. The Principal Investigator, [name], a physician board certified in Physical Medicine and Rehabilitation, will supervise the medical and safety aspects of the study and will be available should an emergent need arise. If for any reason [name] is not immediately available should an emergency arise then the RMD medically responsible physician of the day will be available to assist. In addition, all subjects will be screened by medical history and examination to exclude those with contraindications to exercise. Subjects will be monitored during the exercise tests by an EKG. Subjects will be informed of the signs and symptoms of heart disease and questioned frequently during the test regarding the presence of symptoms of cardiovascular, neurological, or musculoskeletal conditions. Subject’s oxygen saturation will be monitored by infrared pulse oximetry. Safety procedures will be rehearsed by the laboratory personnel and emergency precautions will be observed continuously. A fully equipped emergency response team will be readily available to respond to life threatening events. The current response time is less than three minutes. [name] will be briefed frequently and routinely regarding all testing and training operations. As recommended by the American Heart Association and the American College of Sports Medicine, exercise will be overseen by personnel appropriately trained to extend physician services in the form of exercise testing and training for populations included in this study (non-cardiac disease). Additional clinical consults, e.g, cardiology or pulmonology, along with laboratory testing may be performed in order to help ensure safety for exercise.

Health risks during exercise are very small. In fact may decrease the risk as we are doing intensive peak and submaximal exercise evaluations, performed under controlled and safe clinical conditions as well as other medical tests and examinations related to defining the seriousness of the patients’ conditions. Improvement in aerobic capacity enables individuals to accomplish a given amount of activity or work at a lower percentage of maximum capacity and with less fatigue. Moreover, improvement of exercise tolerance generally increases quality of life by permitting individuals to engage more easily in daily physical activities. It is anticipated that the potential benefits of participating in a program of aerobic exercise conditioning outweigh the minimal risks associated with exercise in this group of patients who have advanced lung disease. Thus, this protocol involves more than minimal risk to study patients, with the prospect of direct benefit to individual subjects.

Participants from Inova Fairfax Hospital’s Advanced Lung Disease Clinic will be identified and referred to the protocol by one of the physician associate investigators. the use and disclosure of patient medical records as an “activity preparatory to research”, the NIH Associate Investigator and Study Coordinator may assist the Inova Principal Investigator, [name], by reviewing medical records of the Inova Advanced Lung Disease (ILD) Clinic and Pulmonary Rehabilitation Department referral patients for purposes of pre-screening Inova patients and patient referrals for this study.

*Consenting:* NIH research staff will interview interested candidates. Those deemed appropriate will both read and sign the NIH approved consent form. A copy of the signed informed consent shall be given to the individual signing the consent and the original consent document will be

retained in the medical record. Upon giving consent, the subject will undergo a full examination by a physician, and a review of available medical records will be performed to confirm their suitability for the trial. After this, they will begin the baseline research tests including: treadmill cardiopulmonary exercise test, arterial occlusion muscle oxygenation capacity test, pulmonary gas exchange analysis, heart rate measurement, bioelectrical impedance plethysmography, near infrared spectroscopy, six-minute walk and fatigability tests, and patient self-report instruments. All tests will be performed again post rehabilitation for outcome comparisons.

### **Data and Safety Monitoring Plan:**

As the PI, [name] will closely monitor patient safety throughout the duration of the study. However, this protocol has several characteristics that suggest a more extensive data monitoring procedure. First, the risk of performing several exercise tests on patients with interstitial lung disease is unknown. We suspect that the risk is a minor increase over minimal risk, but we are not sure. Second, the protocol involves randomization and blinding. Patients will be randomized, to either education or exercise + education. In addition, while the subjects will not be blinded to their treatment allocation, the study personnel will be blinded to the extent that is possible with exercise intervention trials. Study personnel will be blinded through initial baseline screening/testing and randomization, however following randomization due to the nature of exercise training and the time points involved in this study the blinding process will no longer be possible. Finally, this study involves one extramural site: Inova Fairfax Hospital..

Given these additional factors, we feel that our plan may need more than just PI monitoring, but fails to meet the criteria for the involvement of a full DSMB. Therefore, we have enlisted the assistance of [name], MPH, Chairman of the Department of Physical Medicine and Rehabilitation at the Montefiore Medical Center/Albert Einstein College of Medicine, New York, as the independent medical monitor (IMM) for this study. He will be apprised of all significant adverse events. In addition, this monitor will also have access to the study data. RMD's Epidemiology and Biostatistics Department will examine the results on an interim basis. If, at any point, they feel that the study should be stopped because of concern for safety of study subjects, they will inform the PI, the IRB, and the clinical and scientific directors of CC and NHLBI.

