**Specific Aim 2:** “Characterization of the Cardiorespiratory Adaptation to AET in Patients with ILD.” Measures of cardiorespiratory capacity are often influenced by subjective factors such as motivation and confidence. Our measures of cardiorespiratory capacity in this project are AT-time, and muscle oxygenation capacity. Neither of these physiological measures is influenced by subjective factors. We will measure AT-time during tCPET and muscle oxygenation by arterial occlusion testing at baseline and after the AET+ and control regimens. We will also measure Qt, peak VO2, PETO2 and PETCO2 during tCPETs at baseline and after the AET+ and control regimens. We will measure all of the variables again after the group initially completing the control regimen completes the crossover AET regime. We hypothesize:

- 2.1. After the AET+ regimen, AT-time will be significantly prolonged over controls.
- 2.2 After AET+, a significant increase in muscle oxygenation capacity will be observed over controls.
- 2.3 Qt, peak VO2, PETCO2 and PETO2 will remain unchanged following both AET+ and control regimens.
- 2.4 In the Sub-study on Crossover we hypothesize that AET will result in improvements over baseline in all of the variables of interest including AT-time and muscle oxygenation that are similar to AET+. We also hypothesize that Qt, peak VO2, PETO2 a PETCO2 will remain unchanged over baseline after AET.

**Specific Aim 3:** “Determination of the Influence of AET on Patient-reported Measures of Fatigue, Physical Activity, and Other HRQoL Domains in Patients with ILD.” We will use the Fatigue Severity Scale (FSS) to assess fatigue severity, Human Activity Profile (HAP) to assess participation in physical activities, SF-36v2 to assess general HRQoL, Profile of Mood States (POMS) to assess changes in mood, and Kings Brief Interstitial Lung Disease Health Status Questionnaire (K-BILD) to assess HRQoL specific to ILD. We will also use the St. Georges Respiratory questionnaire to assess HRQoL specific to IPF. Subjects will answer the questionnaires before and after the AET+ and control regimens. Subjects in the group receiving the control regimen will again answer the questionnaires after completing the crossover AET regimen. We hypothesize

- 3.1. After AET+, fatigue severity will be diminished over control.

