Primary data obtained from the symptom limited treadmill exercise tests includes  $VO_2$  from pulmonary gas exchange analysis, heart rate (HR) from EKG, cardiac output from bioelectrical impedance cardiography (ZCG), and muscle oxygenation from near infrared spectroscopy (NIR). Additional supporting data will also be available from these devices. Infrared pulse oximetry and blood pressure will also be monitored during the treadmill tests. Data from the pulmonary analysis system, EKG, ZCG, and NIR will be collected continuously throughout the tests. This is a symptom-limited test in which the target stopping point is volitional exhaustion, defined as the subject's expressed desire to stop despite strong encouragement from the testing staff. Other symptomatic endpoints for stopping the tests will be those recommended by the American College of Sports Medicine. Additionally should any subject's oxygen saturation desaturate to  $\leq 80\%$  the test will be terminated at this point with or without the presence of symptoms of severe dyspnea.

Blood glucose of diabetic patients will be monitored before and after testing, and as clinical necessary. Testing will be performed by qualified staff using NIH glucometer or using patient's own glucometer. In order to use patient's own glucometer, it must first be validated for accuracy through the NIH Department of Laboratory Medicine.

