Pulmonary Gas Exchange Analysis: Pulmonary gas analyses will be performed using computerized system including rapid response oxygen and carbon dioxide analyzers, and a pneumotachometer interfaced with a microprocessor will be used for measurement of cardiorespiratory gas exchange. Subjects will interface the system using a mouthpiece or facemask that is connected to a plastic pneumotachometer. A plastic tube connects the pneumotachometer to the gas analysis system. When using a mouthpiece, subjects will also wear a nose clip to prevent expired air from escaping through the nostrils. Gas exchange variables measured during the tests will be measured continuously, on a breath-by-breath basis. Data reduction methods may utilize numbers bin or serial rolling averages. The dependent variable of interest obtained from gas analyses is  $VO_2$ .  $VO_2$  will be determined from the Haldane equation. Volume of expired carbon dioxide ( $VCO_2$ ) will also be measured and used in the calculation RER, where  $RER = VCO_2/VO_2$ . Attainment of an RER of at least 1.10 is one of criteria indicating that oxidative metabolism is approaching a physiologically maximum level at volitional exhaustion.

Heart Rate Measurement: Heart rate will be obtained from EKG recordings. Electrodes will be placed on the subjects' chests in the standard Mason-Likar exercise-testing configuration. EKG will be monitored and recorded continuously throughout the maximum exercise test.

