use or the patient began using supplemental oxygen during the exercise training, all post-training exercise tests will be performed with the same oxygen device/flow used in the baseline testing to maintain consistency between tests.

Blood glucose of diabetic patients will be monitored before and after training, or as clinically appropriate. If training at NIH CC, glucose monitoring will be performed by qualified staff using NIH glucometer or patient's own glucometer (if first validated for accuracy through the NIH Department of Laboratory Medicine). If training at Inova Fairfax, blood glucose monitoring will be performed per Inova policy.

The locations for this intervention will be Inova Fairfax Hospital and the NIH CC. At NIH, the intervention will take place in the Clinical Center Fitness Center located in room 7-3551 on the 7th floor of the Clinical Center and will be led by trained NIH AI staff. This room has three treadmills that are currently used for aerobic training of CC patients.

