### **Analysis**

Our statistical model for specific Aims 1-3 will compare variables of interest between and within the AET+ and CON groups at baseline and post-intervention with a 2-way mixed model analysis of variance (2-way ANOVA). Should there be baseline differences in the specific variable of interest or in demographic characteristics, we will use an analysis of covariance (ANCOVA) to control for the group equality, but the study will be powered under the assumption that no informative covariates are identified and using 6MWT as the primary outcome.

In Specific Aim 1 we will test the hypothesis that AET+ will improve scores on measures of PWC. The dependent variables for this Aim include total distance covered and fatigability index on the 6MWT, and peak WR achieved on the tCPET. 6MWT distance is the primary outcome variable for this RCT and thus our project is powered on the sample size estimated to achieve a significant outcome on this variable (See Sample Size below).

In Specific Aim 2, we will test the hypothesis that after AET+, significant increases in AT-time and muscle oxygenation will be observed over CON. The main dependent variables for this aim are AT-time and measures of muscle oxygenation which include [Tot-Hb], [O2-Hb], [H-Hb], and StO2 measured during tCPET and muscle arterial occlusion cuff tests. Additional dependent variables will include Qt and its components HR and SV measured during tCPETs.

In Specific Aim 3 we will test the hypothesis that patients will report decreased fatigue severity, increased physical activity, and improvements in other HRQoL. The dependent variable score for fatigue severity will be the Fatigue Severity Scale score. The dependent variable score for physical activity will be the Human Activity Profile maximum and average scale scores, and the scores for HRQoL will be composite and domain scores for the SGRQ-I, SF-36v2, and K-BILD.

In the crossover sub-study, we will determine if AET+ induces significant improvements in the variables of interest in the CON group. For this analysis we will use repeated measures ANOVA’s to determine differences in the variables of interest among baseline, 10-week post control, and 2-week post crossover AET data points. Dependent variables will be those in each of the specific aims characterized above.

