Based on this recruitment goal we have agreed upon the following strategy to maintain an effective end power. At which point we attain 45 completed subjects (total) an analysis of the standard deviations in 6MWD from pre to post will be determined in the control and intervention cohorts. To maintain the blinding controls of the study as much as possible, this analysis will be performed by our statistician only. Based on this analysis our sample size will be adjusted thereafter to reflect a more accurate sample size needed to maintain an effective end power.

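### Personnel blinding is declared impossible after randomisation, yet the stored recordings behind AT-time and the STI slope could be read masked, and the rules for deriving both are left open

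*Combined protocol and SAP*

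**What the plan says.** **Blinding.** Under Data and Safety Monitoring Plan, personnel are to be blinded as far as an exercise trial allows, through baseline testing and randomisation. After that, "following randomization due to the nature of exercise training and the time points involved in this study the blinding process will no longer be possible". Patients know their arm throughout: "while the subjects will not be blinded to their treatment allocation". One later control appears under Sample Size, for the look at standard deviations at 45 completers: "To maintain the blinding controls of the study as much as possible, this analysis will be performed by our statistician only".

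**Endpoints.** For Aim 2, the Analysis section states: "The main dependent variables for this aim are AT-time and measures of muscle oxygenation". Under Arterial Occlusion Muscle Oxygenation Capacity Test, the rate of decline in STI is named as the main muscle tissue saturation measure.

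**Derivation.** Under Pulmonary Gas Exchange Analysis: "Data reduction methods may utilize numbers bin or serial rolling averages". No bin size or averaging width is given. The occlusion lasts at most 10 minutes, and no window or fitting method is given for the slope. No section says how the anaerobic threshold is identified or by whom.

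**Data.** The treadmill test section has gas-exchange, EKG, impedance and near-infrared signals collected continuously. The Data Management Plan moves laboratory data to a network folder open only to the principal and associate investigators.

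**The concern.** The plan sets itself the standard of blinding where possible, then treats exercise training as ruling it out for every later task. Training makes the arm obvious to the patient and to whoever supervises the sessions. It does not make the arm visible in a breath-by-breath or near-infrared file that carries a neutral code.

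At stake are hypotheses 2.1 and 2.2, the between-arm claims for AT-time and muscle oxygenation. Randomisation protects against differences between the patients in the two arms. It does not protect against a difference introduced when values are extracted by someone who knows the arm. The exposure is greater where the extraction rule is open, because a choice of averaging, threshold or fitting window can be made test by test.

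**Working it through.** The documents give no reader error, standard deviation or power figure for AT-time or the STI slope. The only power figures are for 6MWT distance and do not bear on this point. The check is therefore mainly a comparison of sections.

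**1. Do the stated reasons cover the reading of files?**

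| Reason in the monitoring plan | Patient or trainer | Reading a stored file |
|---|---|---|
| Nature of exercise training | Reveals the arm | Does not reveal the arm if the file is recoded |
| Time points of the study | Control patients stay for a crossover phase | Baseline and first retest after 10 weeks occur in both arms (Overview of the Research Paradigm) |

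One timing feature needs care. Only control patients have a third test, after the crossover. A reader who receives all of a patient's files together could infer the arm from their number. Coding each test separately and hiding the visit removes that clue.

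**2. What is left to choice?**

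| Endpoint | Source | Fixed | Open |
|---|---|---|---|
| AT-time | Gas exchange during the treadmill test | Breath-by-breath recording | Bins or rolling averages, their width, the threshold rule, the reader |
| Rate of STI decline | Near-infrared signal during cuff occlusion | Formula for the index | Slope window, method of fit, the reader |

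**3. Does another section close the gap?** The Data Management Plan gives each subject a protocol number, but this does not mask arm or visit. The statistician-only look at 45 completers concerns the variability of walk distance and takes place after values have been extracted. The independent randomiser protects allocation. No section provides masked files, a masked reader or a second reader.

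**4. How sensitive is the test to a reading difference?** This is an illustration with assumed biases. With two time points, the group-by-time test of the mixed ANOVA is equivalent to a two-sample t test on change. Let b be the arm-dependent reading bias in standard deviations of the change score, with n = 30 per arm, no true effect and two-sided alpha 0.05:

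- noncentrality = b × √(n/2) = b × √15 = 3.873b, with 30 + 30 − 2 = 58 degrees of freedom
- type I error = P(|T| > critical value), with T noncentral t

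| b (assumed) | Noncentrality | Type I error |
|---|---|---|
| 0 | 0 | 5.0% |
| 0.1 | 0.39 | 6.7% |
| 0.2 | 0.77 | 11.9% |
| 0.3 | 1.16 | 20.8% |
| 0.5 | 1.94 | 47.8% |

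Nothing in the documents shows which row applies, or that b differs from zero.

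**The case against.** The strongest reply is that these are secondary endpoints, no reader is identified, and the threshold may be found by software under one rule. That is fair as to weight. If extraction were fully automatic under a fixed rule, knowledge of the arm would matter little. The plan does not say so, however, and fixing the rule is part of what is asked.

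A reader might also infer several stronger points that the documents do not support:

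- **That all blinding is abandoned.** Blinding holds through baseline testing and randomisation, and the statistician-only look is a further control.
- **That the averaging option also covers the near-infrared slope.** That sentence stands in the gas-exchange section. For STI, the open choice is the slope window and fit.
- **That the plan contradicts itself in saying "Neither of these physiological measures is influenced by subjective factors".** In its context under Specific Aim 2, this refers to the participant's motivation and confidence. It makes no claim about the person reading the file.
- **That trainers test their own patients.** The Exercise Training section says of the NIH sessions that they "will be led by trained NIH AI staff", but no section says who runs or reads the follow-up tests. Some patients train at Inova Fairfax, while all testing is at NIH.
- **That coaching biases the walk distance.** The stopping rule that refers to the subject's "expressed desire to stop despite strong encouragement from the testing staff" belongs to the treadmill test and does not appear in the 6MWT description. Walk distance is not read from a stored signal, and any percentage shift in it would be invented.

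**Conclusion.** The point holds in a limited form. The statement that blinding is no longer possible after randomisation is not justified for deriving AT-time, other gas-exchange values and STI slopes from stored files. No masked reading is planned, and the extraction rules are incomplete for both main Aim 2 endpoints. Bias is possible; it is not shown. Its size cannot be determined from the documents, and the type I error table rests entirely on assumed values of b. The primary endpoint, 6MWT distance, is not affected by this point. The change is worth making because it protects main secondary endpoints at small cost, not because the trial's main comparison is at risk.

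**What to change.** Amend the Data and Safety Monitoring Plan so that the loss of blinding is limited to patients and to staff who deliver or supervise the regimens. Then add:

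1. AT-time, other gas-exchange values and near-infrared/STI slopes are derived by an existing team member from files recoded test by test to hide arm and visit.
2. The key is held by someone who does not read the files, for example the statistician.
3. One averaging method and width, and one rule for identifying the anaerobic threshold, are fixed under Pulmonary Gas Exchange Analysis for all tests.
4. One slope window and method of fit for STI are fixed under Arterial Occlusion Muscle Oxygenation Capacity Test for all tests.
5. Values are locked before unmasking.

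Tests already recorded can be re-read under the same rules while their files exist.

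The cost is protocol wording plus modest recoding and key-holding work. Because folder access is restricted to investigators, the recoded copies and the key need a separate arrangement. Sample size, alpha, visits and patient care are unchanged. Changes to staff rostering or test coaching are not needed for this point.
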